10.2 Protocol Deviations

10.2.1 Important Protocol Deviations

Analysis set: SAF

The following summary tables and listings of important protocol deviations will be provided (separately for pre-/post inclusion deviations):

- Frequency table per reason of important protocol deviations
- Listing of important protocol deviations

10.2.2 Reasons Leading to the Exclusion from an Analysis Set

Not applicable since no Per-Protocol population was defined for any parts of this study.

11 Demographics and Other Baseline Characteristics

Analysis set: SAF

11.1 Demographics

Demographic characteristics will be summarized by using the following information from the "Demography" eCRF pages.

Demographic characteristics

- Sex: male, female
- Race: white, black or African American, Asian, American Indian or Alaska Native, Native Hawaiian or Other Pacific Islander, not collected, other
- Ethnicity: Hispanic or Latino, Not Hispanic or Latino, not collected
- Ethnicity (Part A2): Japanese, Not Japanese
- Age (years): summary statistics
- Age categories :
 - o < 65 years, ≥ 65 years

 - 65-74 years, 75-84 years, ≥85 years
- Pooled Region:
 - North America
 - Europe
- BSA at Baseline: summary statistics

Specifications for computation:

Age (years):

- (date of given informed consent date of birth + 1) / 365.25
- In case of missing day for at least one date, but month and year available for both dates:
 For the derivation of age, the day of informed consent and the day of birth will be set to 1 and the formula above will be used
- In case of missing month for at least one date, but year available for both dates:
 For the derivation of age, the day and the month of informed consent and the day and month of birth will be set to 1 and the formula above will be used
- BSA (m²) = ([height (cm) x weight (kg)] / 3600)^{1/2}

Site codes will be used for the determination of the subject's geographic region.

All relevant demographic data will be presented in data listings.

11.2 Medical History

Analysis set: SAF

The medical history will be summarized from the "Medical History" eCRF page, using the latest version of Medical Dictionary for Regulatory Activities (MedDRA), preferred term (PT) as event category and MedDRA system organ class (SOC) body term as Body System category.

Medical history will be displayed in terms of frequency tables: ordered by primary SOC and PT in alphabetical order.

A supportive listing of medical history data by subject will include all the relevant data fields as collected on the "Medical History" eCRF pages.

11.3 Prior Anti-cancer Treatments and Procedures

Analysis set: SAF

The prior anticancer treatments and procedures are collected from the "Prior Anti-cancer Therapy" (Parts A and B1), "Prior Anti-cancer Drug Therapy Details" (Part A2), "Prior Radiotherapy" (Parts A and B1), "Prior Anti-cancer Radiotherapy Details" (Part A2), and "Prior Cancer Surgery" (Parts A and B1) eCRF pages.

The summary of prior anti-cancer treatments and procedures will include the following:

- Number of subjects with at least one prior anti-cancer therapy
- Type of therapy: chemotherapy, hormonal therapy, immunotherapy, investigational therapy, or other
- Regimen number of prior anti-cancer therapy: neoadjuvant, adjuvant, regimen 1 to regimen 10, or unknown
- Best response to regimen from prior anti-cancer therapy: complete response (CR), partial response (PR), stable disease (SD), progressive disease (PD), not evaluable (NE), or unknown
- Time elapsed since most recent anti-cancer therapy (months): summary statistics
- Duration of most recent anti-cancer therapy (months): summary statistics

Summary of prior radiotherapy will include the following variables:

Number of subjects with at least one prior radiotherapy

 Location: brain, breast, lung, pleura, head and neck, esophagus, spinal cord, vertebrae, lymph nodes, bone, or other

The following listings of prior anti-cancer therapies will also be provided:

- Listings of prior anti-cancer therapies
- Listing of prior radiotherapies
- Listing of prior cancer surgeries (Parts A and B1 only)

These will include subject identifier and all the relevant data collected on the corresponding eCRF pages.

11.4 Other Baseline Characteristics

Analysis sets: SAF

Information on other baseline characteristics are collected from the "Vital Signs," "WHO Performance Status" (Parts A and B1), "ECOG Performance Status" (Part A2), "Primary Malignancy" (Parts A and B1), and "Disease History" (Part A2) eCRF pages. Disease characteristics collected at the pre-treatment evaluation visit will be summarized. Summary statistics will be presented for the following:

- Height at Baseline (cm): summary statistics
- Weight at Baseline (kg): summary statistics
- Body mass index (BMI) at baseline (kg/m²): summary statistics
- Eastern Cooperative Oncology Group (ECOG) performance status: 0, 1, 2, 3, 4
- Summary of primary malignancy including the following:
 - o Number of subjects with at least one primary malignancy
 - Primary malignancy: non-small cell lung cancer, small cell lung cancer, breast cancer, ovarian cancer, colorectal cancer, prostate cancer, or other
 - Histopathological grade of primary malignancy: G1/Well differentiated, G2/Moderately differentiated, G3/Poorly or undifferentiated, GX/Grade cannot be assessed, or other
 - TNM staging at diagnosis: T, N, M and associated sub-categories
 - o Stage at diagnosis: IA, IB, IIA, IIB, III, IIIA, IIIB, IV, or other
 - Time elapsed since time of primary malignancy (months): summary statistics

Specifications for computation:

• BMI (kg/m²) = weight(kg)/[height(m)]²

Baseline characteristics with respect to vital signs, physical examinations, and hematology/biochemistry will be part of Section 15 (Safety Evaluation).

All relevant baseline characteristics data will also be presented in data listings.

12 Previous or Concomitant Medications/Procedures

Analysis sets: SAF

12.1 Previous Medications

Previous medications are medications, other than trial medications and pre-medications for trial drug, which started before first administration of trial drug (M4344 or carboplatin, as applicable), regardless of when dosing of the medication ended.

Previous medications will be summarized from the "Prior and Concomitant Medications" eCRF page. Anatomical Therapeutic Chemical (ATC)-2nd level and preferred term will be tabulated as given from the latest version of World Health Organization-Drug Dictionary (WHO-DD). In case multiple ATCs are assigned to a drug, all ATC-2nd level will be used for reporting. In case the date values will not allow to unequivocally allocate a medication to previous medication, the medication will be considered as previous medication.

All reported previous medications will be listed.

12.2 Concomitant Medications

Concomitant treatments are medications, other than trial medications, which are taken by subjects any time on-trial (on or after the first day of trial drug treatment for each subject) or within 30 days after last dose of trial drug.

Concomitant treatment will be summarized from the "Prior and Concomitant Medications" eCRF page. ATC-2nd level and preferred term will be tabulated as given from the WHO-DD current version. In case multiple ATCs are assigned to a drug, all ATC-2nd level will be used for reporting. In case the date values will not allow unequivocal allocation of a medication as a concomitant medication, the medication will be considered a concomitant medication.

Medications that started before the first dose of a trial drug (M4344 or carboplatin, as applicable) and continued after the first dose of a trial drug will be summarized as previous medications and separately as concomitant medications.

All relevant concomitant medication data will be listed.

12.3 Concurrent Procedures

All concurrent procedures, which were undertaken any time during the trial, will be summarized according to the eCRF page "Non-Pharmacological Treatment or Procedures" (Parts A and B1) or "Concomitant Procedures" (Part A2).

Concurrent procedures will be derived in the same way as concomitant medications. In case the date values will not allow unequivocal allocation of a procedure as a concurrent procedure, the procedure will be considered a concurrent procedure.

All concurrent procedure data will be listed, including flags for procedures that took place prior to, on or after the date of first dose of a trial drug (M4344 or carboplatin, as applicable), or within 30 days after the last dose of a trial drug (M4344 or carboplatin, whichever was taken last).

13 Treatment Compliance and Exposure

Analysis set: SAF

Dosing information is collected from the "Study Drug Administration: VX-803 – Clinic Dose" (Parts A and B1), "Study Drug Administration Home Dose: VX-803" (Parts A and B1), "Study Drug Administration: Carboplatin" (part B1 only), "End of Dosing" (Parts A and B1), "M4344 Time of Administration" (Parts A2), and "M4344 Administration Details" (Part A2) eCRF pages.

- Part A: M4344 is taken twice a week (on treatment days 1, 4, 8, 11, 15, and 18) of a 21-day treatment cycle.
- Part A2: M4344 is taken twice a day every day of a 21-day treatment cycle. Once daily dosing and additional cohorts with a planned drug holiday may also be explored.
- Part B1:
 - Carboplatin is administered by infusion on treatment day 1 of a 21-day treatment cycle
 - M4344 is taken on treatment days 2 and 9 of a 21-day treatment cycle. An additional cohort with one additional dose on day 5 may be explored.

Total number of administrations of M4344

Total number of administrations is calculated as the sum of administrations that a subject received across cycles where actual dose received is > 0 mg or the eCRF field for "Did the subject take the dose of VX-803?" on the "Study Drug Administration Home Dose: VX-803" is marked as "Yes" or if the eCRF field for "Was VX-803 administered?" on the "Study Drug Administration: VX-803 – Clinic Dose" is marked as "Yes."

Total number of infusions of carboplatin (part B1 only)

Total number of infusions is calculated as the sum of the actual number of infusions that a subject received across cycles, regardless of infusion delays, interruptions, or any other deviations from the protocol required schedules. An infusion is regarded to be administered if either the actual dose received is > 0 mg or the duration of the infusion is > 0 minutes.

Total cumulative dose

Total cumulative dose for a study drug is the sum of the actual dose amount that a subject receives across cycles.

- M4344: The total cumulative dose (mg) is the sum of the actual dose amount across all cycles. The individual actual dose (mg) is taken from the "Dose level administered (mg)" field from the "Study Drug Administration: VX-803 Clinic Dose" and "Study Drug Administration Home Dose: VX-803 Part A" (Parts A and A2) or "Study Drug Administration Home Dose: VX-803 Part B/C" (Part B1) at each dosing day.
- Carboplatin: The total cumulative dose (mg) is the sum of the actual dose amount taken
 from "Scheduled dose to be administered in mg" if "Was entire dose administered?" is
 answered as "Yes" on the "Study Drug Administration: Carboplatin" eCRF page. If "Was
 entire dose administered?" is answered as "No" then the result from "If no, actual volume
 given (mL)" will be used

Total planned dose

For each study drug, total planned dose (mg) is calculated based on the initial planned dose as follows:

Initial planned dose on the first dosing day (mg/administration) × number of planned administrations/cycle × treatment duration (weeks) / 3 (weeks/cycle)

For each study drug the values for initial planned dose (mg/administration) and number of planned administrations/cycle are according to the planned dose level/schedule treatment group. The treatment duration is derived for each study drug at subject level, as defined below.

Duration of therapy

Treatment duration will be calculated differently based on the dosing days and frequency as follows:

Part A: During each 21 day cycle, M4344 is taken twice a week on treatment days 1, 4, 8, 11, 15, and 18. Duration of M4344 therapy is calculated as follows:

Duration of M4344 (weeks) =
$$\left(\frac{\text{date of last dose-date of first dose} + 4}{7}\right)$$

Part A2: During each 21 day cycle, M4344 is taken twice a day, every day of the treatment cycle. Duration is calculated as follows:

Duration of M4344 (weeks) =
$$\left(\frac{date\ of\ last\ dose-date\ of\ first\ dose+1}{7}\right)$$

Part B1: During each 21 day cycle carboplatin is administered by intravenous infusion on treatment day 1 and M4344 is taken on treatment days 2 and 9. Duration of M4344 and carboplatin is calculated as follows:

Duration of M4344 (weeks) =
$$\left(\frac{date\ of\ last\ dose-date\ of\ first\ dose+14}{7}\right)$$

Duration of Carboplatin (weeks) =
$$\left(\frac{\text{date of last dose-date of first dose} + 21}{7}\right)$$

Dose intensity

M4344

Dose intensity (mg/3 week) =
$$\left(\frac{Total\ Cumulative\ dose\ of\ M4344\ (mg)}{(duration\ (in\ weeks)/3)}\right)$$

Carboplatin

Dose intensity (mg/3 week) =
$$\left(\frac{Total\ Cumulative\ dose\ of\ carboplatin\ (mg)}{(duration\ (in\ weeks)/3)}\right)$$

Relative dose intensity

The relative dose intensity (%) is calculated based on 3-week cycles for each study drug by dividing the dose intensity by the planned 3-weekly cumulative dose of the appropriate study drug.

The following summary tables will be provided:

- Duration of therapy (weeks) and by subgroups of ≤ 3 weeks, > 3 6 weeks, > 6 9 weeks,
 > 9 -12 weeks, > 12 weeks
- Total number of administrations
- Total number of infusions (for carboplatin in Part B1)
- Total cumulative doses (mg)
- Dose intensity (mg/3 week)
- Relative dose intensity (%) and by subgroups of < 60%, ≥ 60% < 80%, ≥ 80% < 90%, ≥ 90% ≤110%, >110%

Dose reductions

Dose reduction is defined as less than 90% dose compliance at a single dose. Dose compliance is calculated, for each dose received, as the percentage of actual non-zero dose (mg) received with respect to the initial planned dose on Cycle 1 Day 1.

Minimum dose compliance will be derived for each subject (across all of the subject's non-zero doses received) as follows:

Minimum dose compliance (%) =
$$\left(\frac{100 \, x \, actual \, non-zero \, minimum \, dose \, amount \, (mg)}{initial \, planned \, dose \, (mg)}\right)$$

The minimum doses of the trial drugs will be derived per subject and categorized according to a < 50%, \geq 50% - < 70%, \geq 70% - < 90%, \geq 90% level of the planned dose. Subjects with minimum dose compliance \geq 90% are considered to have no dose reductions.

Therapy Delays

Therapy delays will be derived for M4344 and carboplatin in Parts A and B1 based on study drug administration date. Delays will be grouped into the following categories based on the deviation to the planned treatment administration day (relative to the previous treatment administration date):

- No delay (including 1-2 day delays)
- 3-8 day delay
- 9-15 day delay
- >= 16 day delay

All relevant trial drug exposure data will be presented in data listings, including dose reduction or delay reasons.

14 Efficacy Analyses

Analysis set: FAS

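### For an incomplete carboplatin infusion the plan enters the volume in mL, unconverted, into a dose in mg, so Part B1 cumulative dose, dose intensity and RDI are wrong for those subjects

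*SAP*

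**What the plan says.** The text is in Section 13 (Treatment Compliance and Exposure) of the plan for Parts A, A2 and B1.

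- **Unit.** "Carboplatin: The total cumulative dose (mg) is the sum of the actual dose amount taken", so the total is in mg.
- **Complete infusion.** The amount is taken "from 'Scheduled dose to be administered in mg' if 'Was entire dose administered?' is" answered Yes. This is a field in mg.
- **Incomplete infusion.** If the same question "is answered as 'No' then the result from 'If no, actual volume" "given (mL)' will be used". This is a field in mL, and no conversion follows.
- **Downstream use.** Carboplatin dose intensity is the cumulative dose divided by (duration in weeks / 3). RDI is dose intensity divided by the planned 3-weekly dose. All three quantities are planned summary tables.
- **Dose reduction.** "Dose reduction is defined as less than 90% dose compliance at a single dose". Compliance is the mg received at each non-zero dose as a percentage of the planned Cycle 1 Day 1 dose. This paragraph names no eCRF field for the mg received.

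The neighbouring M4344 rule draws on a field recorded in mg, so the problem is specific to carboplatin.

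**The concern.** The two branches of one rule have different units, and the result carries the unit of only one of them. Interrupted or incomplete infusions are the cases that an exposure table has to describe correctly, and they are the only cases in which the mL field is used. A subject's recorded carboplatin exposure would then depend on how dilute the bag was. The error runs upward for dilute bags and downward for concentrated ones, so no single correction could be applied afterwards.

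Part B1 has safety and tolerability of M4344 with carboplatin as a primary objective. A reader would use these tables to judge how much carboplatin subjects tolerated.

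**Working it through.** The plan states no numerical result here, so there is no figure to reproduce. The check applies the plan's own formulas to an incomplete infusion entered in two ways.

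**Inputs from the plan (Section 13).** One carboplatin infusion on Day 1 of each 21-day cycle; duration in weeks = (last dose date − first dose date + 21) / 7; dose intensity = cumulative dose / (weeks / 3); RDI = dose intensity / planned 3-weekly dose; a reduction is compliance below 90%.

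**Assumptions (not in the documents).** Scheduled dose D = 500 mg, equal to the initial planned dose at every cycle; concentration c from 0.5 to 10 mg/mL; fraction infused f. The percentages do not depend on D.

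**Size of the error per infusion.** The prepared volume is D/c, so the volume given is f × D/c mL. The true dose is f × D mg. The literal entry is therefore the true dose divided by c, and the two agree only at c = 1 mg/mL.

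**Subject level: four cycles, one infusion half given.** Duration = (63 + 21)/7 = 12 weeks, and 12/3 = 4. True cumulative dose = 3 × 500 + 250 = 1750 mg; dose intensity = 1750/4 = 437.5 mg per 3 weeks; RDI = 437.5/500 = 87.5%. The literal cumulative figure is 1500 + 250/c.

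| c (mg/mL) | Literal cumulative | Literal dose intensity | Literal RDI | Plan's RDI band (true: 80 to <90%) |
|---|---|---|---|---|
| 0.5 | 2000 | 500 | 100% | 90 to 110%: wrong |
| 1 | 1750 | 437.5 | 87.5% | unchanged |
| 2 | 1625 | 406.25 | 81.25% | unchanged |
| 4 | 1562.5 | 390.6 | 78.1% | 60 to <80%: wrong |
| 10 | 1525 | 381.25 | 76.25% | 60 to <80%: wrong |

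**Single-dose compliance, if the mL value is carried over.** Literal compliance is 100 × f/c.

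| True compliance | c = 0.5 | c = 2 | c = 10 |
|---|---|---|---|
| 30% | 60% | 15% | 3% |
| 50% | 100% (reduction missed) | 25% | 5% |
| 80% | 160% (reduction missed) | 40% | 8% |
| 95% | 190% | 47.5% (false reduction) | 9.5% (false reduction) |

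In the unmarked cells the yes/no reduction status is right. In general, for c < 1 a true reduction is missed when 0.9c ≤ f < 0.9. For c > 1 a false reduction appears when 0.9 ≤ f < 0.9c; once c exceeds 1/0.9 ≈ 1.11 mg/mL, that covers every incomplete infusion of 90% or more. The plan's compliance category is wrong more often than the status. At c = 2, for example, true values of 50% and 80% both fall into the below-50% category.

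**The case against.** **Intent is plainly mg.** The total is labelled mg and described as the actual dose amount, and the infusion-count rule refers to an actual dose above 0 mg. The sentence on the mL field can be read as leaving out a conversion step rather than as ordering mL to be added to mg. That is a fair reading of intent, but it does not rescue the rule. A document meant to give detailed specifications names a field in the wrong unit and supplies no input from which to convert. If the prepared volume is not collected, programming cannot repair it silently.

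**The magnitude is assumed.** The documents give no concentration, scheduled dose or frequency of incomplete infusions. This stands. The figures show mechanism and range and do not predict an effect. The subject-level effect can also be modest: at 2 mg/mL the RDI in the example stays in its band.

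**Stronger readings that the document does not support.** A reader might infer that dose-reduction status is wrong for every incomplete infusion. It is not: a true 80% remains a reduction at 2 and at 10 mg/mL, and is lost only in the 0.5 mg/mL column. A reader might also take it as stated that the mL value feeds dose compliance. The plan only implies this, since the mL field is the sole source that it offers for an incomplete infusion. Nor does the problem reach the dose-finding conclusions. DLT evaluability in Part B1 requires the Day 1 carboplatin dose without a mg threshold (Section 8.2), the MTD uses the DLT flag on the adverse event page (Section 15.1), and the PK parameters are for M4344 (Section 16.1).

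**Conclusion.** The concern holds as a wrong stated rule, not as missing detail. For Part B1 subjects with an incomplete carboplatin infusion, cumulative dose, dose intensity and RDI are wrong unless the concentration is 1 mg/mL. Each such infusion is off by a factor 1/c. In the four-cycle illustration, a true RDI of 87.5% becomes anything from 76.25% to 100% over the assumed 0.5 to 10 mg/mL. Misclassification of compliance category and reduction status is possible rather than certain, and depends on the mL value also being used there.

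The reach is limited to descriptive carboplatin exposure tables in one study part. M4344 exposure, the number of infusions, DLT/MTD and PK are unaffected. It should be fixed, but it does not threaten the primary conclusions.

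**What to change.** Replace the incomplete-infusion branch in Section 13 with: actual dose (mg) = scheduled dose (mg) × volume given (mL) / total prepared volume (mL). State that this mg value is used for both cumulative dose and dose compliance.

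If the prepared volume is not on the eCRF, obtain it by query before database lock. If it cannot be obtained:

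- flag the infusion and list the recorded volume;
- set that subject's cumulative dose, dose intensity, RDI and minimum dose compliance to missing;
- do not count the infusion as zero, and do not drop it from the minimum, because dropping it could label a subject with a truly reduced infusion as having no reduction.

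The cost is a short wording change, a small programming change, and one query per incomplete infusion whose prepared volume is not on record. The documents do not say how many there are.

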^a Subsequent time point is not necessarily the direct subsequent scan (e.g. PR-SD-PR will have PR as confirmed BOR).

Both confirmed and unconfirmed BOR will be summarized by tabulating the number and percentage of subjects with CR, PR, SD, PD, or NE as BOR.

A swimmer plot displaying key radiological milestones will be produced by dose group and study part. For each subject, the time from treatment start until end of follow-up will be represented (from treatment start to last date known to be alive or date of death). In addition, following information will be displayed: time to confirmed BOR (CR, PR or SD), time to progression, and status at the end of the follow-up (alive or dead).

Objective response rate (ORR) is defined as the proportion of subjects having achieved a BOR of PR or CR (summarizes as objective response [OR]) according to RECIST version 1.1. Both CR and PR must be confirmed by repeat assessments performed no less than 4 weeks after the criteria for response are first met.

ORR will be summarized by visit along with the 2-sided 90% confidence interval (CI) using the Clopper-Pearson (1) method (exact CI for a binomial proportion as computed by default by the FREQ procedure using the EXACT option).

Disease control rate (DCR) is defined as the proportion of subjects having achieved a BOR of CR, PR, or SD according to RECIST version 1.1.

The DCR will be summarized by visit along with the 2-sided 90% CI using the Clopper-Pearson (1) method (exact CI for a binomial proportion as computed by default by the FREQ procedure using the EXACT option).

Tumor shrinkage will be summarized as the percent change in target lesions (sum of diameters of all target lesions for non-nodal lesion and short axis for nodal lesion) per time point from baseline. The tumor response will be based on the investigator assessment and derived as follows:

(Sum of target lesions at Week XX – sum of target lesions at baseline) / sum of target lesions at baseline x 100%

The maximum reduction in target lesions from baseline will be derived across all the post-baseline assessments until documented disease progression, excluding assessments after start of a subsequent anti-cancer therapy, derived as follows:

Minimum of ((sum of target lesions at Week XX – sum of target lesions at baseline) / sum of target lesions at baseline) x 100%

The percent change from baseline in target lesions per time point as well as other relevant information will be presented in a data listing.

A waterfall plot of maximum percent reduction from baseline in the sum of diameters of target lesions for each subject with measurable disease at baseline and at least one valid post-baseline assessment will be provided. The waterfall plot will show the bar for the subject with the largest positive change on the left, and the bar for the subject with the largest negative change on the right.

The listing of tumor assessments (including e.g. lesion number, description and location, type of lesion, imaging date, assessment method, diameter (mm), sum of diameter of target lesions (mm), BOR (confirmed and unconfirmed) will be provided by subject as recorded from the "Imaging Scan Disease Assessment - Target Lesions" (Parts A and B1), "Imaging Scan Disease Assessment - Non-Target Lesions", "Imaging Scan Disease Assessment - New Lesions" (Parts A and B1), "Imaging Scan - Overall Response Assessment" (Parts A and B1), "Sum of Diameters (According to RECIST 1.1)" (Part A2), "Tumor Assessment - Target Lesions" (Part A2), "Tumor Assessment - Non-Target Lesions" (Part A2), and "Tumor Assessment - New Lesions" (Part A2) eCRF pages.

15 Safety Analyses

The subsections in this section include specifications for summarizing safety endpoints that are common across clinical trials such as AEs, laboratory tests and vital signs.

